10.10.1 AE and Concomitant Medication Start and Stop Dates

Start Date: If only 'day' is missing, and the month and year are not the same as the month and year of the first dose, then day will be imputed with '01'. Otherwise, if the month and year are the same as first dose date, first dose date will be used. If 'day' and 'month' are missing, and 'year' is not missing, then month and day will be imputed with month and day of first dose date (assuming same 'year'). If the start date is completely missing, then the first dose date will be used. If the stop date is complete and the imputed start date is after the stop date, then the imputed start date will be set to the stop date. The original, non-imputed, dates will be retained in the clinical trial database and will be included in subject listings.

Stop Date: If only 'day' is missing, day will be imputed with last day of the month. If 'day' and 'month' are missing, and 'year' is not missing, then month will be imputed with '12' and day will be imputed with '31' (or date of study discontinuation/completion if earlier than Dec-31 and year is the same as the year of discontinuation). If the stop date is completely missing, it will be set to the date of study discontinuation/completion. A stop date will not be applied to ongoing AEs. If the imputed stop date is greater than the last contact date, then the imputed stop date will be set to last contact date. The original, non-imputed, dates will be retained in the clinical trial database and will be included in subject listings.

10.11 Missing Data

10.11.1 Missing Neutrophils

When a neutrophil value is missing, if values for segmented cells (SEGS) and bands (BANDS) are available, neutrophils will be calculated as:

SEGS+BANDS

If the neutrophil value is missing and either SEGS or BANDS are available, the neutrophil value will be the non-missing value of SEGS or BANDS.

10.11.2 Missing Absolute Differential

See section [10.10.3 Differential](#) above.

10.12 Completed Trial

All subjects who remain on trial through their End of Study Visit and listed as "Subject Completed Study" will be considered as having completed the trial.

11.0 Analysis Sets

In all analysis sets, individual subjects will be grouped by dose according to the initial dose assigned.

11.1 Safety

The safety analysis set comprises all subjects who receive at least one dose of onvansertib and will be used in the analysis of safety variables.

11.2 Intention-to-Treat

The Intention to Treat (ITT) analysis set comprises all subjects who received at least one dose of study treatment (onvansertib and at least one dose of either low-dose cytarabine or decitabine) These subjects will be used in the analysis of efficacy variables.

11.3 Per Protocol

Subjects in the ITT analysis set who complete at least one cycle of study treatment, have had ≥ 1 evaluable post-baseline tumor assessment (BM) and have no important protocol deviations that have the potential to affect efficacy will be included in the PP analysis set.

11.4 Pharmacokinetics

The PK analysis set will consist of all subjects in the safety analysis set who have adequate plasma onvansertib concentration data as determined by the PK scientist.

12.0 Interim Analyses

Not applicable. There is no formal interim analysis planned for this study. However, the Safety Review Committee, consisting of the Principal Investigators and Medical Monitor, will monitor subjects for safety and to evaluate efficacy of onvansertib doses to minimize exposure of subjects to a non-efficacious dose level.

13.0 Statistical Methods

All statistical analyses will be performed using SAS® Version 9.4 or higher.

Summaries will be presented by dose level and total within each combination (onvansertib + decitabine or onvansertib + low-dose cytarabine) at each dose enrolled, except for demographic data which will be presented by Phase but not individual dose levels. PK summaries will not include totals combining dose levels.

Subjects who have intra-subject dose escalation will be summarized in their initial dose group.

Categorical variables will be summarized using counts and percentages. Percentages will be rounded to one decimal place except 100% will be displayed without any decimal places and percentages will not be displayed for zero counts.

Continuous variables will be summarized using the number of observations (n), mean, standard deviation, median, minimum, maximum, 25th and 75th percentiles. The mean, median, and quantiles will be presented to one more and the standard deviation to 2 more decimal places than the precision of the original variable, while the minimum and maximum will be presented at the same precision as the original variable.

13.1 Subject Disposition

The count and percentage of subjects screened, enrolled and treated in the study will be presented, along with the count and percentage of subjects included in each analysis set. The count of subjects who discontinue the study along with a breakdown of the corresponding reasons for discontinuation will also

be summarized in the safety analysis set. The count and percentage of subjects enrolled at each site will also be summarized based on all subjects enrolled. All visits and treatment assignments of the safety set will be presented in the listings. Discontinuations from study will be presented in listings.

13.2 Demographic and Baseline Characteristics

Demographics including age (years), age categories, sex, race, ethnicity, height (cm), weight (kg) and BMI (kg/m^2) will be summarized at baseline using the safety analysis set. An additional demographics table will be generated for the PP analysis set

The number of weeks from AML diagnosis to the first dose of study drug, prior therapy use (yes/no), weeks from last prior AML therapy to the first dose of study drug, relapse status (yes/no), weeks from relapse to first dose, weeks from last AML therapy to relapse, and progression status (yes/no) will be summarized for the safety analysis set. Additionally, ECOG PS will be summarized. Prior AML therapy data will be listed by subject.

Medical history and physical examination results will be presented in listings in the safety analysis set.

13.3 Treatments

13.3.1 Extent of Study Drug Exposure

Study drug exposure will be summarized descriptively based on the safety analysis set for the following variables:

- Duration of exposure (months)
- Number of cycles administered for each study treatment
- Total dose administered (mg/m^2) calculated for each study treatment
- Number of dose adjustments (increase and decrease) per subject (onvansertib) with reason for dose adjustment
- Number of dose interruptions per subject (decitabine)
- Duration of dose interruptions per subject (minutes) (decitabine)
- Number of missed doses per subject for each study drug.

A listing will present exposure data by subject for onvansertib administration for the safety analysis set. Separate listings will present exposure data for low-dose cytarabine and decitabine administration based on the safety analysis set.

13.3.2 Concomitant Medications

Using the safety analysis set, the count and percentage of subjects using at least one concomitant medication overall will be summarized along with the count and percentage of subjects using at least one concomitant medication for each PT.

All medications will also be listed for the safety set. In the listing, medications will be classified as prior, prior and concomitant or concomitant.

13.4 Important Protocol Deviations

Protocol deviations will be identified, including, but not limited to, subjects that were enrolled even though they did not meet all eligibility criteria, subjects who took concomitant medications specifically prohibited by the protocol, and subjects who received the wrong study drug or an incorrect dose. The reason for each protocol deviation will also be identified.

Per PRA processes, important protocol deviations data will be entered into our Clinical Trials Management System (CTMS). The study team and the Sponsor will conduct ongoing reviews of the deviation data from CTMS and the resulting set of PP subjects throughout the study, adjusting the deviation criteria as appropriate. The PP analysis set must be finalized at the post-freeze data review meeting (or earlier), prior to database lock.

For each study phase, important protocol deviations for subjects in the safety analysis set will be summarized by deviation category. Important protocol deviations will also be listed. A Data listing will also present all protocol deviations by subject including whether deviation is an important protocol deviation resulting in exclusion from PP analysis set.

13.5 Efficacy Analyses

Inferential statistical analysis comparing efficacy data among onvansertib dose levels or historical data is not planned.

Subjects from the ITT analysis set will be included in the efficacy analyses. Similar summaries will also be generated for the PP analysis set.

Primary efficacy summaries will be generated for Phase 2 subjects. Derived efficacy data for Phase 1b and Phase 2 subjects will be presented in Subject listings.

13.5.1 Leukemic Response

The primary efficacy variable is leukemia response in Phase 2 subjects as evaluated by the Investigator at the end of each induction cycle, as indicated by the Investigator, and at the end of -study visit based on BM aspirate and peripheral blood examination results.

Responders are subjects with a CR or CRi accompanied by MLF state. Subjects without efficacy evaluable assessments will be considered non-responders in the ITT analysis population.

The count and proportion of Phase 2 subjects achieving CR, CRi, MLF state, PR, Stable Disease, or Treatment Failure as the best overall leukemic response will be summarized based on the ITT analysis set using counts and percentages.

Rate of complete response (CR+CRi) will be summarized for the ITT analysis set and exact 95% binomial confidence intervals generated.

The count of subjects with MLF state and PR will be summarized based on counts and percentages for the ITT analysis set. All efficacy tables will also be presented for the PP analysis set. Ninety-Five% exact CIs will be presented for the percentages. Similar summaries will be generated based on extramedullary disease.

BOR data will be provided in a listing.

13.5.2 Duration of Response

DOR will be summarized using Kaplan-Meier (KM; [Kaplan and Meier 1958](#)) estimates for the ITT and PP analysis set in Phase 2 subjects who have had a response (CR, CRi, MLF state, or PR). The min, max, 25%, 50%, and 75% quartiles will be calculated and corresponding 95% CIs for the quartiles by the KM method. A KM plot for DOR will be presented. The count and percentage of responding subjects who have an event or are censored will be summarized.

DOR data will be provided in a listing.

13.5.3 Event-Free Survival

EFS will be summarized using KM estimates for the ITT and PP analysis set in Phase 2 subjects. The min, max, 25%, 50%, and 75% quartiles will be calculated and corresponding 95% CIs for the quartiles by the KM method. A KM plot of EFS will be presented. The count and percentage of those who have an event or are censored will be summarized. The EFS rate at 12 months and corresponding 95% CIs by the KM method will be presented.

EFS data will be provided in a listing.

13.5.4 Overall Survival

Overall Survival (OS) will be summarized using KM estimates for the ITT and PP analysis sets in Phase 2 subjects. The min, max, 25%, 50%, and 75% quartiles will be calculated. A KM plot of OS will be presented. The count and percentage of subjects who have an event or are censored will be summarized. The OS rate at 12 months and corresponding 95% CIs will be presented by the KM method.

OS data will be provided in a listing.

13.5.5 Exploratory Efficacy Analyses

Select individual components from BM aspirate results, BM aspirate response, and other parameters used to assess disease response will be listed for the ITT analysis set and the PP set.

13.6 Safety Analyses

Data from all subjects who receive at least one dose of study drug (onvansertib) will be included in the safety analysis.

Inferential statistical analysis comparing the safety data among onvansertib dose levels or with historical data is not planned.

13.6.1 Adverse Events

Safety will be assessed primarily based on AEs. All summaries of AEs will be based on treatment-emergent AEs unless otherwise indicated.

Counting of AEs will be by subject, not by event; subjects will be counted only once within each SOC or PT.

The count and percentage of subjects who report AEs will be summarized by phase and dose cohort for the safety analysis set as follows:

- AEs that are DLTs
- AEs by SOC and PT
- AEs by SOC, PT, and maximum NCI-CTCAE grade
- NCI-CTCAE Grade ≥ 3 AEs by PT
- Serious AEs by SOC and PT
- AEs related to onvansertib by SOC, PT, and maximum NCI-CTCAE grade
- NCI-CTCAE Grade ≥ 3 AEs related to onvansertib by PT
- Serious AEs related to onvansertib by SOC and PT
- AEs leading to discontinuation of study medication
- AEs with an outcome of death

For grade summaries, subjects with multiple events within a particular SOC or PT will be counted under the category of their most severe event within that SOC or PT. Events will be sorted by descending frequency of the total across all dose cohorts by SOC, and by PT within SOC for summaries.

AEs and TEAEs will be listed for individual subjects, including information regarding onset, duration, severity, seriousness, outcome and relationship to study drug.

13.6.2 Deaths

AEs with an outcome of death will be listed. In addition, death data from the survival status CRF will be presented in a listing. Causes of death will be included.

13.6.3 Laboratory Data

All laboratory results (hematology, clinical serum chemistry and urinalysis) will be presented in listings.

Shift tables for some hematology and chemistry tests will be provided for the maximum post-baseline grade including data from any unscheduled post-baseline timepoint, and the last study assessment while on study treatment. These tables will compare the NCI-CTCAE grade for the baseline value relative to each post-baseline time point value for all non-missing post-baseline data.

13.6.4 Vital Signs

A summary of abnormal vital signs by time point will be presented, where abnormal vital signs are systolic blood pressure >140 mmHg, diastolic blood pressure >90 mmHg, heart rate <60 beats/min or >100 beats/min, or temperature >37.5°C.

Vital sign results will be provided in data listings.

13.6.5 Physical Examinations, ECGs, and Other Observations Related to Safety

Additional safety assessments include physical examinations, ECG measurements, ECOG performance status, pregnancy tests and multigated acquisition (MUGA) or echocardiography (ECHO) scans.

Summaries of the above safety assessments are described below. Only listings will be generated for physical examination and pregnancy test results.

13.6.5.1 ECG

A summary of average of triplicate ECG parameters, heart rate, P-R interval, QRS interval, QT interval, QTcF interval and RR interval and change from baseline will be presented for each planned visit.

The count and percentage of subjects who have abnormal QTcF during the study will be summarized by the following International Conference on Harmonization (ICH) E14 categories:

Male:

QTc interval > 450 ms
QTc interval > 480 ms
QTc interval > 500 ms

Female:

QTc interval > 480 ms
QTc interval > 500 ms

Change from baseline in QTc interval:

QTc interval increases from baseline > 30 ms
QTc interval increases from baseline > 60 ms

All triplicate and average ECG data will be provided in data listings.

13.6.5.2 ECOG Performance Status

For Phase 1b and Phase 2, shift tables comparing ECOG data from baseline to post-treatment follow up/EOS ECOG score will be generated.

All ECOG data will be provided in data listings.

13.6.5.3 ECHO/MUGA

ECHO/MUGA results will be summarized based on shifts between screening and post-treatment follow up/EOS, with shift tables generated using normal/abnormal categories and normal/abnormal non-clinically significant abnormal/abnormal clinically significant categories.

ECHO/MUGA results will be presented in a listing.

13.7 Pharmacokinetic Analyses (PK)

13.7.1 Pharmacokinetic Variables

Concentrations of onvansertib will be collected in plasma.

PK parameters of onvansertib will be calculated for plasma.

13.7.2 Plasma Pharmacokinetic Summaries

13.7.2.1 Plasma Concentrations

The lower limit of quantification (LLOQ) of onvansertib is 0.100ng/mL. Plasma concentrations onvansertib below the quantifiable limit (BQL) will be set to 0 in the computation of mean concentration values. Descriptive statistics (number of subjects, mean, geometric mean, standard deviation (SD), coefficient of variation [%CV], median, min, and max) will be used to summarize the plasma concentrations by phase, cycle, combination drug and dose at each scheduled time point.

Semi-logarithmic (+SD) plots of the arithmetic mean plasma concentration by scheduled sampling time will be provided by phase, cycle, combination drug and dose. These plots will show time in hours. The plots will present all calculated means and will include a reference line for LLOQ.

All individual subject plasma concentration data will be listed by subject, by phase, combination drug and dose.

13.7.2.2 Plasma Pharmacokinetic Parameters

Plasma PK parameters for onvansertib will be estimated using non-compartmental methods with WinNonlin® version 8.1 using Best Fit regression. The PK parameters will be estimated from the concentration-time profiles, and AUCs will be calculated using linear up / log down method. In estimating the PK parameters, BQL values will be set to zero. Actual sampling times, rather than scheduled sampling times, will be used in all computations involving sampling times. If the actual time is missing, the scheduled time will be substituted and flagged.

In estimating the PK parameters, BLQ values at the beginning of the profile will be set to 0. BLQ values that occur after the first quantifiable point will be considered missing. Values that are embedded between BLQs, or quantifiable values occurring after two or more BLQs, will be set to missing at the discretion of the PK specialist

The following flags will be used to include parameters that meet the predefined criteria for summary and analysis:

Criteria Name	Analysis Flag	Criteria
Regression	ANL02FL	Adj Rsq ≥ 0.8

Note: Flags will be applied to parameters prior to derivation of additional parameters in SAS and will be used to include derived parameters as well.

The plasma concentration of onvansertib administered in combination with low-dose cytarabine or decitabine will be collected at specified study timepoints measured according to the schedule outlined in Tables 9-1, 9-2, and 9-3 of the protocol and reported by timepoint for onvansertib. The following PK parameters will be calculated as applicable for each subject:

Table 3. PK Parameters

Parameter	Description	Cycle, Day	SAS Programming Notes
Cmax	Maximum plasma concentration. Observed peak analyte concentration obtained directly from the experimental data without interpolation, expressed in concentration units	Cycle 1, Day 1, Cycle 1, Day 5, Cycle 2, Day 1, Cycle 2, Day 5	Cmax from WNL
Ctrough	Observed plasma concentration at the end of each dosing interval	Cycle 1, Day 5, Cycle 1, Day 8, Cycle 1 Day 15, Cycle 1, Day 22, Cycle 2 Day 5, Cycle 2 Day 8, Cycle 2 Day 15, Cycle 2 Day 22	Pre-dose concentration on for Cycle 1 on Day 5, 8, 15 and 22 and Cycle 2 on Day 5, 8, 15 and 22 from ADPC. Calculated in SAS.
Tmax	Time to maximum plasma concentration. First observed time to reach peak analyte concentration obtained directly from the experimental data without interpolation, expressed in time units.	Cycle 1, Day 1, Cycle 1, Day 5, Cycle 2, Day 1, Cycle 2, Day 5	Tmax from WNL
AUClast	Area under the concentration-time curve (time 0 to time of last quantifiable concentration).	Cycle 1, Day 5, Cycle 2, Day 5	AUClast from WNL
AUCtau	Area under the concentration-time curve over the dosing interval (time 0 to 24hr). If the nominal 24hr concentration was taken at or after 24hr postdose then AUCtau will be calculated by WNL to 24hr. If the nominal 24hr concentration was taken before 24hr post-dose and a valid λz is available then the data will be extrapolated to 24hr. If the nominal 24hr concentration was taken before 24hr post-dose and a valid λz is not available then AUC0-24 calculated to actual time will be used for AUCtau.	Cycle 1, Day 1, Cycle 1, Day 5, Cycle 2, Day 1, Cycle 2, Day 5	AUClast from WNL for Cycle 1 Day 1 and Cycle 2 Day 1 AUCtau from WNL Cycle 1 Day 5 and Cycle 2 Day 5 In case when AUCtau might not be available in WNL file, summary file might be used to extract the parameters for 24h nominal sampling time
T-HALF	Terminal phase half-life expressed in time units	Cycle 1, Day 5	HL_Lambda_z from WNL
CLss/F	Apparent clearance at steady state	Cycle 1, Day 5	CLss_F from WNL
Vss/F	The apparent volume of distribution during the terminal phase is calculated by dividing Dose by the product of AUCtau and λz .	Cycle 1, Day 5	Vz_F from WNL

Descriptive statistics (number of subjects, mean, geometric mean, SD, %CV, median, min, and max) will be used to summarize the calculated PK parameters by phase, cycle, combination drug and dose. For Tmax, only median, min and max will be presented.

All parameters will be listed by subject, by phase, cycle, combination drug and dose; parameters that meet the inclusion criteria will be accompanied by an indication that each is criteria met.

The following parameters will be used for diagnostics and thus listed but not summarized.

Parameter	Description	SAS Programming Notes
Adj Rsq	Goodness of fit statistic for the log-linear terminal elimination phase of the concentration-time profile identified by least-squares linear regression and adjusted for the number of points (minimum of 3) used in the estimation of Lz.	Rsq_adjusted from WNL
Lz	Terminal phase rate constant calculated by linear regression of the terminal log-linear portion of the concentration vs. time curve. Using no weighting factor, the terminal log- linear phase of the concentration-time curve is identified by least-square linear regression of at least 3 data points that yielded a maximum G criteria, which is also referred to as adjusted R2. Lz is the absolute value of the slope of the terminal log-linear phase. Note: In Phoenix, use Best Fit method to determine regression.	Lambda_z from WNL

13.8 Pharmacodynamic and Diagnostic Biomarkers

Polo-like kinase 1, % blasts (serum and BM), and tumor gene expressions will be measured periodically during the study. Results will not be transferred to PRA and will not be included in the TFL deliveries.

13.9 Methods for Handling Dropouts and Missing Data

In Phase 1b, subjects who are discontinued prior to completing the first treatment cycle for any reason other than toxicity, or who have not received at least 80% of the intended doses without experiencing a DLT will be replaced. Data for subjects who are replaced will not be included in the summary analyses; data for replaced subjects will be presented in separate data listings. Sensitivity analyses of response parameters including all subjects (with replaced subjects analyzed as non-responders) may be generated as deemed appropriate per study results. Censoring rules for time to event endpoints are specified in Sections [10.6.5](#) to [10.6.7](#). Rules for imputation of missing/partial dates and other missing data are specified in Sections [10.10](#) and [10.11](#).

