9.4 Safety Assessments

Toxicity will be graded using the National Cancer Institute Common Terminology Criteria (NCI-CTCAE version 4.03).

- Safety analysis will be conducted on all subjects who have received at least one dose of study drug, and will include the frequency of all AEs and laboratory abnormalities as well as the frequency of dose interruptions, dose reductions, and treatment discontinuation.
- In Phase 1b, DLTs will be considered to be any non-hematologic Grade 3 abnormalities that persist >7 days without decreasing in severity despite standards of care, are clinically significant, or that are Grade 4 and symptomatic. Exceptions and additional parameters for assessment of non-hematologic DLTs are provided in the protocol. For hematologic toxicities, only persistent pancytopenia resistant to current standards of care that continues for ≥ 42 days and is not related to leukemic infiltration or another cause unrelated to study therapy will be considered as a DLT, since marrow aplasia is an expected consequence of AML therapy.
- Any subject that has not completed a full initial cycle and received at least 80% of study drug due to issues other than DLTs, including disease progression, will be replaced.

Additional safety assessments will include physical examination; medical history; ECG; ECOG performance status; weight; vital signs measurements; clinical laboratory testing (hematology, clinical chemistry, and urinalysis) and MUGA or ECHO scans.

Safety assessments will be performed as per the Schedule of Assessments ([Section 9.1](#)). Safety assessment may be performed at additional time points during the study at the discretion of the Investigator in the interest of subject safety.

The SRC, consisting of the Principal Investigators and Medical Monitor, will monitor subjects for safety and to evaluate efficacy of onvansertib doses to minimize exposure of subjects to a non-efficacious dose level.

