12.3 Statistical Analysis of Efficacy Data

Data from all subjects who receive at least one dose of onvansertib in combination with either cytarabine or decitabine will be included in the intention-to-treat (ITT) efficacy analysis. Subjects completing at least one cycle of treatment will be included in the per protocol efficacy analysis.

The efficacy endpoints for this study include CR, CRi, PR, MLF, DOR, and OS. Further description of the efficacy measurements and response criteria for this study is presented in [Section 9.3.1](#).

Descriptive statistics will be generated as appropriate (ie, mean, median, range, and SD). Median survival statistics will be estimated using the Kaplan-Meier Time-to-Event.

Inferential statistical analysis comparing efficacy data among onvansertib dose levels or historical data is not planned.

The primary efficacy endpoint is the rate of CR + CRi in the Phase 2 portion of the study. Based on a population CR + CRi rate of 20% for either the combination of cytarabine plus onvansertib or decitabine plus onvansertib, with 32 evaluable patients in the primary analysis the 90% CI for the CR + CRi rate from the study will have an estimated precision of approximately 58% and width 0.23, and a 95% CI would have an estimated precision of approximately 70% and width 0.28.

PK parameters to be determined will include C_{max} , T_{max} , AUC_{0-24} , and $t_{1/2}$, which will be estimated from plasma concentration data. The geometric mean and 95% CIs will be reported for all evaluable subjects.

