6.1 Changes from Protocol

The definition of the per protocol analysis set differs from the protocol by requiring at least one post baseline efficacy assessment (bone marrow) and also excluding subjects who have important protocol deviations that have the potential to affect efficacy. Efficacy endpoints from investigator response on bone marrow aspirate response form in CRF differ from the endpoints reflected in the protocol. Additional choices of stable disease and treatment failure are available in the CRF. These efficacy endpoints are incorporated into the statistical sections of this SAP and the TFL shells.

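### SAP 13.9 drops replaced Phase 1b subjects from the summary analyses, which contradicts the Safety set and, secondarily, the PK set; SAP 6.1 does not declare it

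*SAP*

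**What the plan says.** SAP 13.9 first describes who is replaced in Phase 1b: a subject who leaves before the end of Cycle 1 for a non-toxicity reason, or who has less than 80% of the intended doses and no DLT. It then says: "Data for subjects who are replaced will not be included in the summary analyses". Their data go to separate listings. A sensitivity analysis that includes them is optional, covers response only, and is to be decided in the light of the results.

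The analysis sets say otherwise:

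- Safety, SAP 11.1: "The safety analysis set comprises all subjects who receive at least one dose of onvansertib". SAP 13.6 repeats it: "Data from all subjects who receive at least one dose of study drug (onvansertib) will be included in the safety analysis". Protocol 12.2 has the same sentence, and Protocol 9.4 agrees: "Safety analysis will be conducted on all subjects who have received at least one dose of study drug".
- PK, SAP 11.4: "The PK analysis set will consist of all subjects in the safety analysis set who have adequate plasma onvansertib concentration data".
- ITT, SAP 11.2: the set "comprises all subjects who received at least one dose of study treatment", meaning onvansertib plus a partner drug. Protocol 12.3 matches: "Data from all subjects who receive at least one dose of onvansertib in combination with either cytarabine or decitabine will be included".

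SAP 6.1 lists the departures from the protocol. It begins "The definition of the per protocol analysis set differs from the protocol" and adds the extra response categories on the CRF. It does not mention replaced subjects.

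**The concern.** A replaced subject can have been dosed, and can have been dosed enough to have adverse events and a PK profile. The 80% limb of SAP 13.9 catches a subject whose doses were cut short by a toxicity that was not a DLT. Under 13.9 that toxicity would be missing from the Phase 1b AE table; under 11.1 and 13.6 it would be counted. A programmer has to choose, and the SAP gives no order of precedence.

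The tables at stake are the Phase 1b discontinuation breakdown (13.1), exposure (13.3.1), AEs (13.6.1) and PK summaries (13.7.2). The first three are specified on the safety set. Phase 1b AE incidence and severity is a primary endpoint in SAP 9.1, although SAP 9.2 lists the same item as secondary. SAP 13.0 asks for results by dose level, where denominators are small.

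**Working it through.** **Step 1. The passages side by side, for a dosed Phase 1b subject who is replaced**

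| Output | Set named for the output | In or out by that set | In or out by SAP 13.9 |
|---|---|---|---|
| Discontinuations by reason (13.1) | Safety | In | Out |
| Exposure (13.3.1) | Safety | In | Out |
| AE tables (13.6.1) | Safety | In | Out |
| PK summaries (13.7.2) | PK (11.4) | In, if concentrations are adequate | Out |
| Response, DOR, EFS, OS (13.5.1 to 13.5.4) | ITT, Phase 2 only | Not applicable | Not applicable |

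A subject with full Day 1 and Day 5 sampling who then leaves for progression shows the PK conflict. The last row shows why the ITT conflict is minor: SAP 13.5 summarises Phase 2 and only lists Phase 1b efficacy. The conflict would matter for the exploratory endpoint in all enrolled subjects (SAP 9.3), or for any Phase 1b response summary that is added.

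**Step 2. Size, as illustration.** The documents do not say how many subjects were replaced. Assume one dosed subject is replaced, with n retained subjects of whom k have the event. SAP 13.9 reports k/n. The Safety set gives (k+1)/(n+1) if the replaced subject had the event and k/(n+1) if not.

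- Cohort of 3: 0/3 = 0% against 1/4 = 25.0% (had the event); 1/3 = 33.3% against 1/4 = 25.0% (did not).
- Cohort of 6: 1/6 = 16.7% against 2/7 = 28.6% or 1/7 = 14.3%.
- Arm total with 42 retained (the planned maximum per arm in SAP 8.1, assumed reached) and 12 events: 12/42 = 28.6% against 13/43 = 30.2% or 12/43 = 27.9%.
- Discontinuations, if the replaced subject left the study: the count is low by 1, and k/n is never above (k+1)/(n+1) because k ≤ n. Example: 2/3 = 66.7% against 3/4 = 75.0%.
- Mean missed doses: retained 1, 1, 1 and replaced 0 gives 1.00 against 3/4 = 0.75; retained 0, 0, 0 and replaced 2 gives 0.00 against 2/4 = 0.50.

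**Step 3. Who counts as replaced.** Four wordings are in use:

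- (i) SAP 8.1 and 13.9, Protocol 12.1: early exit for a non-toxicity reason, or under 80% of doses with no DLT.
- (ii) Protocol 11.1: the same, but the 80% limb has no DLT exception.
- (iii) SAP 10.8.2, Protocol 10.1.5: under 80% of the dose, or stopped for something that is not a DLT. The exception attaches most naturally to the second limb.
- (iv) Protocol 9.4: full cycle and 80% not achieved for reasons other than DLTs. This can mean that not both were met, or that neither was met.

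Two test cases:

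- Stopped by a DLT after 3 of 5 doses (3/5 = 60%, below 80%): kept under (i), replaced under (ii), arguably replaced under (iii) as worded.
- Stopped in Cycle 1 by a non-DLT toxicity after at least 80% of doses (4/5 = 80%): kept under (i) and (ii), replaced under (iii), uncertain under (iv).

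**The case against.** The best defence is that 13.9 was meant for the dose-escalation denominator. Leaving replaced subjects out of that count is normal in a 3+3 design, and the per-protocol set already omits subjects who do not complete a cycle. However, the sentence speaks of the summary analyses in general, and SAP Section 11 defines no DLT-evaluable set to which it could be confined.

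It can also be said that nothing is hidden. Replaced subjects are listed, AEs and deaths are listed by subject, SAP 13.1 reports the numbers treated and in each analysis set, and no inferential safety comparison is planned. That stands and limits the harm, but a listing does not correct an incidence table. The optional sensitivity analysis does not help with safety, exposure or PK.

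Three stronger readings are tempting, and the documents do not support them:

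- A reader might infer that AE rates would be understated. The direction depends on whether the replaced subjects had the event, and Step 2 shows shifts both ways.
- A reader might infer that reported response rates would be inflated. No efficacy table specified in SAP 13.5 changes, and 13.5.1 already counts ITT subjects without evaluable assessments as non-responders.
- A reader might treat the two test cases as settled under every wording. The attachment of the DLT exception in (iii) and the sense of (iv) are open.

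**Conclusion.** The contradiction is real and can be confirmed from the text alone. SAP 13.9 conflicts with the Safety set, and secondarily with the PK set, and SAP 6.1 does not declare it. The conflict with ITT is minor. One replaced subject can move a by-dose AE rate by 25.0 percentage points in a cohort of 3 (0% against 25.0%), but by less than 2 points in an arm total of 42 (28.6% against 30.2%). These sizes assume one replaced, dosed subject; the documents give no number, and there may be none at a given dose.

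The point does not extend to the Phase 2 primary endpoint, because the replacement rule in 13.9 is worded for Phase 1b. It does not challenge the DLT counts under 13.9's own wording or the RP2D decision. The inconsistent replacement wordings are a secondary point. They matter here because they decide who would be excluded. This should be fixed before database lock, so that the denominator is not chosen with results in view.

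**What to change.** In the SAP:

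1. Replace the exclusion sentence in 13.9 with: *Replaced subjects are excluded only from the DLT-evaluable set, which is used for 3+3 decisions, the DLT rate and the MTD. They remain in the Safety and ITT sets and, where data are adequate, the PK set, and in the summaries of those sets.*
2. Add the DLT-evaluable set to Section 11.
3. Amend 13.6.1, which now puts the DLT table on the safety set. For Phase 1b that table should use the DLT-evaluable set and all other AE tables the Safety set, with a footnote on the different denominators. Without this, items 1 and 2 would collide with 13.6.1.
4. In any Phase 1b or pooled response summary, count replaced subjects without a response as non-responders, in place of the optional sensitivity analysis.
5. Reconcile SAP 8.1, 10.8.2 and 13.9 now, and Protocol 9.4, 10.1.5, 11.1 and 12.1 at the next amendment, so that the set has one definition. No wording is preferred here.

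The SAP part costs a few sentences and one population flag on data already collected. The protocol part needs an amendment with IRB/IEC approval, and it cannot change who was replaced in Arm A, which is closed. The downside is that DLT and other AE tables will have different denominators, and Phase 1b rates may move either way.
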